5.1. Inclusion Criteria

Patients are eligible to be included in the study only if they meet all of the following criteria at screening:

Patient and Disease Characteristics

- [1] Patients are 18 to 65 years of age (inclusive) at the time of screening.
- [2] Have a diagnosis of chronic migraine as defined by the IHS ICHD-3 beta guidelines (1.3) (ICHD-3 2013), that is, a headache occurring on 15 or more days per month for more than 3 months, which has the features of migraine headache on at least 8 days per month.
- [3] Migraine onset prior to age 50.
- [4] Prior to Visit 1, a history of at least 1 headache-free day per month for the past 3 months.
- [5] From Visit 2 to Visit 3 (prospective baseline period), have a frequency of at least 15 headache days, of which at least 8 must have the features of migraine headache (see definitions in Table CGAI.2). To avoid biased reporting, patients must not be told the number of migraine headache days on which study qualification is based.
- [6] From Visit 2 to Visit 3 (prospective baseline period), have at least one headache-free day.
- [7] From Visit 2 to Visit 3 (prospective baseline period), must achieve sufficient compliance with ePRO daily headache entries as demonstrated by completion of at least 80% of daily diary entries.

Informed Consent and Patient Agreements

- [8] Are able and willing to give signed informed consent.
- [9] Are reliable and willing to follow study procedures, including all follow-up visits.
- [10] Women of child-bearing potential must test negative for pregnancy at the time of enrollment based on a serum pregnancy test.

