^a The eligibility period of the prospective baseline assessment will last from 30 to 40 days. Investigators and patients may have up to an additional 5 days to schedule their Visit 3 appointment (beyond the 40 days); however, eligibility will be based on the 30- to 40-day period.

^b Visit is to include a review of any spontaneously reported adverse events and collection of blood samples for immunogenicity, PK, and CGRP plasma.

^c A neurological exam will be conducted at screening, Month 3 (final visit of double-blind treatment), Months 6, 9, and 12 (open-label treatment), and Month 16/early termination in order to assess for any signs of pre-existing or treatment-emergent neurological abnormalities such as stroke or other cerebrovascular events.

^d Electrocardiograms (ECGs) will be performed at Visit 1, Visit 3, Visit 7, Visit 10, Visit 16, and Visit 18 or early termination. Note: The Visit 3 ECG should be collected prior to blood draws and dosing. Patients must be supine for approximately 5 to 10 minutes before ECG collection and remain supine but awake during ECG collection.

^e Vital signs taken at every office visit will include body temperature, blood pressure and pulse. Blood pressure and pulse will be measured in triplicate in the sitting position and should be measured prior to blood draws. Blood pressure will be assessed by utilizing a calibrated machine.

^f Chemistry labs collected at Visit 3, Visit 7, Visit 10, Visit 13, Visit 16, and Visit 18 or early termination must be fasting. Fasting is defined as no food or drink, except water, for at least 8 hours prior to testing.

g In the event of a positive urine leukocyte esterase result, a repeat urine sample will be collected and shipped to the central laboratory.

^h A positive urine test must be followed by a serum pregnancy test for confirmation.

Immunogenicity and storage sample, and PK blood sampling to be performed at the indicated visits and prior to dose administration if the visit is a dosing visit. Samples will be taken in the event of early termination. Immunogenicity samples also may be collected in the event of a systemic allergic/hypersensitivity reaction (see Section 8.4.3). The exact date and time of the samples should be recorded.

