Q1. Yesterday, did you have a headache that lasted for thirty minutes or more?	Yes	Migraine if at least 2 migraine Criteria As and at least 1 migraine Criterion B are met; or Migraine Criterion C is met.	
	No ^a		
Q2. Enter the total number of hours you had a headache yesterday.	Range 1 to 24	If ≥ 1 the headache will be counted as a headache day.	
Q3. Yesterday, what was the worst headache	Mild		
pain?	Moderate	Migraine Criteria A	
	Severe	Migraine Criteria A	
Q4. Yesterday, was the headache throbbing or	Yes	Migraine Criteria A	
pounding?	No		
Q5. Yesterday, was the headache just on the	Yes	Migraine Criteria A	
right or left side of your head?	No		
Q6. Yesterday, was the headache made worse	Yes	Migraine Criteria A	
by your usual daily activity?	No		
Q7. Yesterday, did the headache come with	Yes	Migraine Criteria B	
sensitivity to light and sound?	No		
Q8. Yesterday, did you feel sick to the	Yes	Migraine Criteria B	
stomach or throw-up with the headache?	No		
Q9. Yesterday, did you have your menstrual	Yes		
period (if female)?	No		
Q10. Yesterday, did you take any medicine	Yes	Medication will only count as headache	
for your headache?		medication on a day a headache occurred.	
	No		
Q11. Yesterday, did you take any medicine	Yes		
for pain other than headache?	No		
Q12. Yesterday, did you experience aura?	Yes		
	No		
Q13. Yesterday, did you experience any	Yes		
warning symptoms (prodrome	No		
symptoms) that a migraine was coming			
other than aura?			
Q14. Yesterday, do you believe you	Yes	Migraine Criterion C	
experienced a migraine AND it was relieved by a triptan or ergot derivative?	No		

^a If "No" is answered for Q1, then the patients will skip Q2 - Q6, and Q14, only answer questions Q7 - Q13 by removing reference to headache.

Primary Measure: Migraine Headache Days

The primary measure is the number of monthly migraine headache days (per 30-day period). A migraine headache day is defined as a calendar day on which a **migraine or probable migraine** occurs.

The primary measure of the number of monthly migraine headache days in each 30-day period will be summarized from daily data for each patient in that period (including approximately 30 days of daily data from the baseline period prior to randomization, 3 months of daily data during double-blind treatment phase, 9 months of daily data during open-label treatment phase, and 4 months of daily data during post-treatment phase).

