The daily data will reflect whether the patients meet the migraine / probable migraine criteria; those data will be aggregated, and the number of migraine headache days will be provided for each of the 30-day periods. In calculating the number of migraine headache days for each period, if the period is not equal to 30 days, the number of migraine headache days will be adjusted by multiplying the number of migraine headache days by (30/x) where 'x' is the total number of non-missing diary days in the period.

For the 4 months of post-treatment period, the monthly intervals will be derived as below:

- Firstly, the 2-month visit interval will be split into two 1-month periods for efficacy measures. If the number of days between 2 visits (visit x+1 date visit x date + 1) is even, the first half will be in the first 1-month period and the second half will be in the second 1-month period. If the number of days between 2 visits is odd, then the days will be split similarly, but the first 1-month period will have 1 day more than the second 1-month period.
- Secondly, after the 2-month visit intervals are split into two 1-month periods, the monthly data will be derived in the same way for each 1-month period as for treatment phase. For patients who discontinued early during post-treatment phase (Study Period V [SP V]), if the date of discontinuation is within 30 days of the previous visit date, all data between the previous visit date and the discontinuation date will go to 1 monthly period; if the date of discontinuation is more than 30 days of the previous visit date, then the first 30 days will be the first monthly period, and the rest will be considered as part of the second monthly period.

This approach to missing ePRO diary data assumed that the rate of migraine headache per day is the same for days with missing and nonmissing ePRO diary days. The same approach will also be applied to secondary and exploratory efficacy measures that are derived from ePRO data.

Additionally, if the compliance rate for a monthly interval is \leq 50%, then all endpoints to be derived from the ePRO diary data for that 1-month period will be considered missing.

For the post-treatment phase, the derived 1-month periods (resulting from splitting the 2-month visit interval) will be treated similarly.

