For a patient who discontinues early in the double-blind (Study Period III [SP III]) or open-label treatment phase (Study Period IV [SP IV]) or post-treatment phase (SP V), compliance rate for the last month of that study period will be calculated with a denominator of 30 days (or the actual number of days in the interval if greater than 30).

For the rest of months and patients, the compliance rate will be calculated as described in Section 5.5.7.

Other Secondary and Exploratory Efficacy Measures

The same approach for adjusting the number of days within each period to a 30-day period and the same approach to imputing monthly data based on compliance as for the primary measure will be applied to all efficacy measures that are derived from ePRO diary data and need normalization to 30-day period, including:

- Number of ICHD migraine headache days is calculated as the number of calendar days in a 30-day period on which a migraine occurs. Probable migraine is excluded.
- **Number of headache days** is calculated as the number of calendar days in a 30-day period on which a headache occurs.
- Number of moderate-severe headache days is calculated as the number of calendar days in a 30-day period on which a headache occurs with a moderate or severe severity.
- **Number of headache hours** is calculated as the total number of headache hours in a 30-day period on which a headache occurred.
- **Number of migraine headache hours** is calculated as the total number of headache hours in a 30-day period on days when a migraine or probable migraine occurs.
- Number of migraine headache days with medication use is calculated as the number of calendar days in a 30-day period on which migraine or probable migraine occurs and abortive medication is used.

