Appendix Table 1. Description of Important Protocol Deviations

Category	Subcategory	Study-specific	Source	Methods of Identification
Informed Consent	ICF not obtained	Initial ICF date is missing or is after (Visit 1 date or Visit 1 lab date)	Programmable - Stats	For all patients, if initial ICF date is missing or after (Visit 1 date or Visit 1 lab date).
Form (ICF)	Improper ICF	ICF not signed prior to initiation of protocol procedures	Non-programmable - Monitor identified	Or determined by study team
		Age <18 or >65 years old at study entry	Non-programmable- Monitor identified	
		BMI ≥40 at baseline	Programmable - Stats	
		Do not meet criteria of at least 15 normalized headache days of which 8 must have features of migraine	Programmable - Stats	Number of normalized headache days <15, or number of normalized migraine headache days < 8
	leal along	At least one headache free day	Programmable - Stats	Number of normalized headache days > 29
Eligibility	Inclusion/ Exclusion	Baseline ePRO compliance <80%	Programmable - Stats	
		Female patients who have a positive serum pregnancy test prior to randomization visit	Programmable - Stats	For randomized female patients, if serum pregnancy test is positive any time prior to Visit 3
		Female patients who have a positive or no serum pregnancy test prior to randomization visit	Non-programmable- Monitor identified	
		Insufficient washout of prohibited migraine preventive medication for at least 30 days prior to Visit 2	Programmable - Stats	Patients must have discontinued such treatment at least 30 days prior to Visit 2.

Category	Subcategory	Study-specific	Source	Methods of Identification
		Insufficient washout of Botulinum toxin A and B at least 4 months prior to Visit 2	Non-programmable- Study team identified	Stats will create the list of patients meet this IPD criteria. Among those, the true IPDs will be manually added into non-programmable excel sheet
		With suicidal ideation (Q4 or Q5) within past month of visit 1.	Programmable - Stats	Randomized patients with answer "yes" for C-SSRS suicidal ideation Q4 or Q5 occurred within past 1 month of visit 1.
		Positive or no urine drug screen prior to randomization	Programmable - Stats	For randomized patients if prior to visit 3, a patient has a positive UDS result and a repeated UDS not done or last repeat UDS is positive or UDS never collected.

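### Unless values are rounded to whole days, the SAP's programmed check of inclusion criterion [6] lists patients with exactly one headache-free day and 31 to 40 diary entries as eligibility deviations, although they meet the criterion

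*SAP*

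**What the plan says.** Protocol 5.1, criterion [6], requires that over the prospective baseline period, Visit 2 to Visit 3, patients "have at least one headache-free day". Criterion [7] sets the diary requirement for the same period at "completion of at least 80% of daily diary entries". Footnote a of the Schedule of Activities (Protocol Appendix 2) allows a further 5 days for scheduling Visit 3, but says that "eligibility will be based on the 30- to 40-day period".

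SAP Appendix Table 1 (Eligibility, Inclusion/Exclusion) has a row for criterion [6]. It is marked as programmable by the statistics group, and its method of identification is "Number of normalized headache days > 29".

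Normalization is defined in SAP 5.4.1. A count is multiplied by 30/x, where x "is the total number of non-missing diary days in the period". The SAP extends this to the other diary measures, number of headache days among them: "The same approach for adjusting the number of days within each period to a 30-day period". No rounding rule is given.

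Under SAP 5.5.3, important deviations are tabulated and listed by randomized arm for the ITT population.

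**The concern.** Criterion [6] is a yes/no question: was there any headache-free day? The programmed check replaces it with a rate per 30 days and compares that rate with 29. The cut-off separates one free day from none exactly when x is 30. When more than 30 days are completed, a single free day is diluted to less than one per 30 days, the scaled headache count rises above 29, and an eligible patient is recorded as having failed.

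At stake is the accuracy of the deviation report. Protocol section 5 permits no waivers of enrollment criteria, and section 7.1.3 requires documented sponsor approval before an inadvertently enrolled patient may continue. A false entry therefore presents a valid enrollment as a breach and may prompt needless queries. The row has no step at which someone confirms the flag. The botulinum toxin, QTcB and liver-test rows of the same table do have one: a programmed list is made first, and the true deviations are then picked out by hand.

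**Working it through.** Inputs:

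- Flag rule: scaled headache days above 29 (SAP Appendix Table 1).
- Scaling: count × 30/x, with x the completed diary days (SAP 5.4.1).
- Eligibility period: 30 to 40 days (Protocol Appendix 2, footnote a).
- Diary floor: 80% of entries (Protocol 5.1, criterion [7]), that is 24 entries in a 30-day period and 32 in a 40-day period.

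Let f be the number of recorded headache-free days. The scaled value is (x − f) × 30/x = 30 − 30f/x.

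**The plan's own cut-off.** With x = 30 and f = 1: 29 × 30/30 = 29.00. This is not above 29, so the patient is correctly not flagged. The cut-off of 29 reproduces for 30 completed days.

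**One free day, other x.** The value is 30 − 30/x, which exceeds 29 exactly when 30/x < 1, that is when x > 30.

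| x | scaled value, f = 1 | flagged | meets [6] |
|---|---|---|---|
| 24 | 23 × 30/24 = 28.75 | no | yes |
| 30 | 29 × 30/30 = 29.00 | no | yes |
| 31 | 30 × 30/31 = 29.03 | yes | yes |
| 32 | 31 × 30/32 = 29.06 | yes | yes |
| 35 | 34 × 30/35 = 29.14 | yes | yes |
| 40 | 39 × 30/40 = 29.25 | yes | yes |

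All ten values of x from 31 to 40 are flagged.

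**Two or more free days.** With f = 2 the value is largest at x = 40: 38 × 30/40 = 28.50. It is never flagged, because that would need x above 60. More free days give lower values.

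**No recorded free day.** x × 30/x = 30 at every x, always flagged.

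**Dependence on period length.** In a 30-day period x cannot exceed 30, so no false flag arises. In a 38-day period the diary floor is 31 entries (0.8 × 38 = 30.4, rounded up), and it is 32 at 39 and 40 days. In those longest periods every diary-compliant patient with exactly one recorded free day is flagged.

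**Dependence on rounding.** Rounded to whole days, all ten values become 29 and no false flag remains. Rounded to one decimal, x = 31 becomes 29.0 and escapes, but x = 32 to 40 stay above 29.

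**The case against.** The best defense is that the SAP deliberately puts the baseline frequency criteria on a 30-day scale. The row above, for criterion [5], also uses normalized counts although [5] is worded as a count between visits. SAP 5.4.1 treats each month as 30 days, and criterion [4] asks for a headache-free day per month. On that scale one free day in 40 is 0.75 per 30 days, and a cut-off of 29 is a coherent, stricter rule. This stands to the extent that the cut-off may be a convention rather than a slip. It does not make the flag correct. Unlike [4], criterion [6] has no monthly qualifier and names the interval between the two visits. The deviation label for [5] mentions normalization; the label for [6] does not. The SAP says it supersedes the protocol's statistical plans, which does not extend to enrollment criteria.

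A second defense is that the SAP describes baseline as "approximately 30 days of daily data from the baseline period prior to randomization". That wording is approximate, and nothing in either document cuts the diary to 30 days.

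A third is that rounding may remove the problem. Whole-day rounding would, so the finding is conditional on its absence; no rule is stated.

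A reader might also infer that the check misses true failures. SAP 5.4.1 says scaling applies "if the period is not equal to 30 days, the number of migraine headache days will be adjusted". Read literally, a 30-day period with 24 to 29 entries and no free day would keep a count of 24 to 29 and pass. The documents do not support this. The same section presents the scaling as its approach to missing diary data, assuming the same daily rate on missing and completed days. That makes sense only if a 30-day period with missing entries is scaled too. The result is then 30 (for example 24 × 30/24), and the patient is caught. In such a patient the days without an entry might also have been headache-free, so failure would not be established.

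**Conclusion.** The check is wrong in one direction and in one narrow group: patients with exactly one recorded headache-free day and 31 to 40 completed baseline diary days. They meet [6] as worded, score 29.03 to 29.25, and would be listed as important eligibility deviations.

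This rests on three assumptions: scaled values are not rounded to whole days, the whole 30- to 40-day eligibility period enters x, and scaling follows completed diary days as SAP 5.4.1 defines them. How many patients are affected cannot be derived, since neither document gives the distribution of baseline length or of headache-free days.

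The point is minor. A reader might infer that eligibility decisions or the efficacy results are compromised. They are not: under SAP 5.5.3 these deviations are only summarized and listed, none of the four populations in SAP 5.5.1.4 is a per-protocol set, and no estimate or test uses the flag.

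**What to change.** Replace the method of identification for the criterion [6] row with a direct count on recorded days: flag the patient if the number of recorded headache days equals the number of completed baseline diary days, that is, if no headache-free day was recorded. This follows the wording of [6] and depends on neither scaling nor rounding. It does not resolve days with a missing entry, which remain unknown as they do under the current check.

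The cost is one programming line and one table cell in the SAP. No new data are needed, and no population or analysis changes. The reported number of eligibility deviations may change.
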